#### *Parkinson's Disease Medication Use*

All subjects in the study will be asked to continue taking Parkinson's disease medication(s) as prescribed by their Parkinson's clinician throughout the duration of this study. Any modifications to medicines made during this study will be based on the clinician's judgment. Changes to medications will be recommended until the patient is considered to be controlled

unless contraindications are identified by the investigator. All PD medications and subsequent changes will be recorded in the medication log CRF. In addition, non-PD prescription medications of anti-depressants, anti-psychotics and blood pressure lowering agents will be tracked in the other medication log CRF.

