#### 4.5 Interim Follow-Up Visits

Interim follow-ups will be completed for subjects who are not considered to be controlled. For PKG- group subjects, controlled means per clinician standard of care assessment and for PKG+ group subjects, this is per the Acceptable Target Range:

	Target Range
Bradykinesia Score (BKS)	Median BKS 23-25 and/or FDS > 7.5
Dyskinesia Score (DKS)	Median DKS 7-9 and FDS < 13

Interim visits can be completed in-clinic or remotely via telephone per institutional requirements. This timeframe may vary depending on a variety of factors such as physician care practices, amount of total medication change needed, subject medication regimen compliance and subject tolerance to medication changes.

Approximately 28 days prior to each planned subject follow-up visit, a PKG Watch will be ordered through the GKC Portal and dispensed to each subject as previously described and PKG report obtained prior to the visit of PKG+ group subjects for investigator review.

For subjects in the PKG+ Group, the site staff will ensure the PKG is available prior to the Interim Follow-up Visit. Protocol required data collection will occur at each follow-up interim visit. A Subject "ON" State Assessment will be completed and changes in medical history and medications will be recorded. Any protocol defined AEs that have occurred will be captured on the AE Reporting CRF (see Section 8). The study investigator will review the PKG provided by GKC prior to the visit and use the information to guide the discussion with the subject during the clinical assessment. PKG results will be recorded in the PKG Reporting CRF. The study investigator will complete the Clinician Assessment CRF to denote patient-reported symptoms, treatable findings, and clinical management planning based on his/her routine clinical assessment procedures along with the PKG information.

For subjects in the PKG- Group, protocol required data collection will occur at each follow-up interim visit. A Subject "ON" State Assessment will be completed and changes in medical history and medications will be recorded. The study investigator will complete the Clinician Assessment CRF to denote patient-reported symptoms, treatable findings, and clinical management planning based on his/her routine clinical assessment procedures. The study investigator will be blinded to the PKG information during interim visits.

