These steps will be repeated for each interim follow-up until the study subject is determined to be controlled or a maximum of the 4-month follow-up visit.

Up to 4 medication changes including at the Baseline visit and up to 3 interim visits will be allowed to get each subject into a “controlled” state. Interim follow-up visits end when PD symptoms have become optimized (considered controlled on oral therapies) per standard of care assessments for PKG- group subjects and per the Acceptable Target Range as published in Pahwa et al., 2018 and no further treatment changes are indicated as assessed by the study investigator and the subject will proceed to the next required study visit at 4-months Follow-Up.

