3.3. Secondary Objective

The secondary objective is to determine the association between frequency of medication changes, the PKG information, and other clinical assessments among participants with and without a PKG report of their PD motor status available to the clinician at the time of evaluation.

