- Dyskinesia Score
- Fluctuation Score
- Percent Time Immobile (PTI)
- Percent Time Tremor Present (PTT)

Evaluation of individual patient and subgroup response from baseline assessed by change in PKG BK or DK scores from baseline to 4 months for controlled (in target range) and uncontrolled (out of target range) in PKG+ and PKG- groups

- Rate of subjects who were uncontrolled at baseline (PKG Summary Scores exceeded targets) and then became controlled at the 4-month visit (PKG Summary Scores reduced to below targets).
- Rate of subjects unresponsive to medication changes (i.e. no change to PKG BK scores with LED increase)
- Rate of subjects who required treatment changes but were unwilling to make changes (this group may not show any impacts to outcomes)
- Rate of subjects who required treatment changes but were contraindicated to make changes (this group may not show any impacts on outcomes)

8. Change in LED from baseline to each interim visit and 4 months

Calculation of Levodopa Equivalent Dose (LED) at each visit for each patient and a comparison of change in LED at each visit for each patient. If a change is made at the scheduled visit, the change is calculated for the next visit (e.g., a change at the BL visit means the subject has started taking the new medication/dose/frequency change the day after the BL visit, etc.) – See Appendix for reference in calculating LED.

Rate and change in PD medications including medication type, dosing, increase, decrease from baseline to interim1, interim2, interim3, and 4 months.

An analysis to look at medication change amount and frequency and impact on outcome of MDS-UPDRS and PKG BKS will be performed. Patients will be ranked by amount of LED change at each visit and grouped by number of times they had medication changes at a visit (e.g. 0, 1, 2 times, etc.) from baseline to the 4 month visit and correlated to the outcome of MDS-UPDRS and PKG score of BKS at 4 months.

- Rate of subjects who were marked as uncontrolled but had no medication changes will be noted.
- Rate of subjects who had medication changes but were less than 100mg LED will be noted.

9. PKG Patient Survey at 4 months

PKG Patient Survey at 4 months. Tabulate values and proportions and changes from baseline to each visit.

The rate at 4 months will be calculated for the PKG+ and PKG- groups for each section of the survey.

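### SAP 3.4 item 8 relates medication change to 4-month scores with no baseline term, so more medication can look harmful when it helps

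*SAP*

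**What the plan says.** SAP 3.4 item 8 states its purpose as follows: "An analysis to look at medication change amount and frequency and impact on outcome of MDS-UPDRS and PKG BKS will be performed". The exposure has two parts. First, "Patients will be ranked by amount of LED change at each visit". Second, subjects are grouped by how many times their medication was changed between baseline and month 4. Both are then "correlated to the outcome of MDS-UPDRS and PKG score of BKS at 4 months". No baseline score enters, and the outcome is not described as a change.

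The item serves the objective in SAP 3.3, which is to "determine the association between frequency of medication changes, the PKG information, and other clinical assessments".

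The protocol ties the exposure to disease state:

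- Parkinson's Disease Medication Use (section 4.2): "Changes to medications will be recommended until the patient is considered to be controlled", unless the investigator finds a contraindication.
- Section 4.5: "Interim follow-ups will be completed for subjects who are not considered to be controlled".
- Section 4.5 again: "Up to 4 medication changes including at the Baseline visit and up to 3 interim visits will be allowed".

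On MDS-UPDRS and BKS, SAP 3.4 item 2 counts a negative change as improvement, so lower is better.

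**The concern.** Medication change is not randomised here. Subjects who start further from control are the ones kept in the titration loop. They are also likely to have higher scores at 4 months simply because they had higher scores at baseline. For BKS in the PKG+ group the link is direct: the target range that decides whether a subject is controlled includes BKS, and BKS is also one of the two outcomes.

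A correlation with the 4-month level therefore mixes two questions: who needed more medication, and what the medication did. A positive correlation could be read as medication increases worsening symptoms when the true effect is beneficial. Item 8 speaks of impact, which invites that reading. The adjusted regression in Protocol 6.4 does not help, because its main predictor is group assignment, not LED change.

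**Working it through.** The documents give no figure for this correlation, so there is nothing to reproduce. The only numerical input they supply is the SD of 13 for change in MDS-UPDRS Total (SAP 3.2). Everything else below is assumed and varied. All figures concern MDS-UPDRS Total; no BKS figure was computed.

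**1. Closed form.** Let true severity be T, observed baseline B = T + e0, and 4-month score Y = T − b·D + e1. D is LED change in units of 100 mg, with SD 1.5 and correlation r with B. b is the true benefit in points per 100 mg. Each error has SD 13/√2 = 9.19 (variance 84.5), so the change score has SD 13 when b = 0. Then:

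- slope of the 4-month level on D = r·σ_T² / (σ_B·1.5) − b
- slope of change from baseline on D = −b − r·84.5 / (σ_B·1.5)
- slope of the level adjusted for B = −b

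with σ_B = √(σ_T² + 84.5).

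Middle case, σ_T = 20, r = 0.4, b = 2: σ_B = √484.5 = 22.01 and σ_B·1.5 = 33.02.

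- Level: 160/33.02 − 2 = 4.85 − 2 = +2.85 (simulated +2.9, Spearman +0.19). This looks harmful.
- Change: −2 − 33.8/33.02 = −2 − 1.02 = −3.02 (simulated −3.0, Spearman −0.31). The sign is right, but regression to the mean overstates the benefit.
- Baseline-adjusted: −2.0, the truth in this model.

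The level slope has the wrong sign whenever the true benefit is smaller than r·σ_T²/(σ_B·1.5):

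| σ_T | r = 0.2 | r = 0.4 | r = 0.6 |
|---|---|---|---|
| 15 | 1.71 | 3.41 | 5.12 |
| 20 | 2.42 | 4.85 | 7.27 |
| 25 | 3.13 | 6.26 | 9.39 |

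For true benefits of 1, 2 and 3 points, that is 24 of 27 cells. The exceptions are b = 2 and b = 3 at σ_T = 15, and b = 3 at σ_T = 20, all with r = 0.2. At r = 0 there is no reversal.

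**2. At about this trial's size.** This simulation has 38 subjects (assumed; 41 were enrolled), baseline SD 18, change SD 13, LED change with mean and SD of 150 mg before truncation at zero, and a benefit of 3 points per 100 mg.

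| LED-baseline correlation | Level has the wrong sign |
|---|---|
| 0.2 | about 47% of trials |
| 0.4 | about 80% |
| 0.6 | about 97% |

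At 0.4 the mean Spearman is +0.14 with the level, −0.27 with change, and −0.22 for the partial correlation given baseline. At 0 the mean with the level is −0.16, the right sign. With no true effect (change SD 12), the level still gives about +0.16 to +0.47 over correlations 0.2 to 0.6.

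For scale, the nominal two-sided 5% threshold is t/√(n − 2 + t²). With n = 41 and t = 2.02 this is about 0.31. With n = 33 (41 less 20%) it is 0.34.

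**3. With treat-until-controlled feedback.** Steps 1 and 2 let LED change depend on baseline only. Protocol 4.5 goes further: subjects who stay uncontrolled keep receiving changes. One assumed version has up to four steps, a mean benefit of 3 points per step and 38 subjects. Its mean correlations were +0.71 with the level, −0.24 with unadjusted change and +0.13 after baseline adjustment, the last with the wrong sign in 78% of trials. Other assumed versions gave +0.66 with the level, −0.25 to −0.38 with unadjusted change, and +0.23 to +0.33 after adjustment, with the wrong sign in about 89 to 97%. The level is the worst of the three, but baseline adjustment does not guarantee the right sign.

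**The case against.** **The text may already mean change.** SAP 3.2 speaks of the change in total MDS-UPDRS at 4 months, and SAP 3.4 opens by saying that secondary outcomes are compared between baseline and 4 months. The MDS-UPDRS outcome in item 8 could therefore be shorthand for the change. This stands in part: a reader might infer that the SAP definitely uses the MDS-UPDRS level, and the documents do not settle that. The BKS wording is harder to read as a change. Sections 3.2 and 3.4 elsewhere say change when they mean it, so item 8 needs to say which it intends.

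**Item 8 does not stand alone.** A reader might take it as the trial's only exposure-response analysis. It is not. Item 7 reports a rate of subjects unresponsive to medication changes, defined by no change in BKS with an LED increase. That rate uses change, which supports the same choice in item 8.

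**The size is assumed.** The documents give no baseline SD, LED distribution, effect per 100 mg or LED-baseline correlation. The simulation in step 2 excludes LED reductions, although item 8 tracks decreases. Subjects can also be out of target through DKS, and the effect of that on LED change is not stated. At a correlation of 0.1 the level has the right sign in 71% of trials. All of this stands, so the percentages are illustrations.

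**It is a minor analysis.** SAP 3.3 speaks of association, and item 8 states no decision rule. That also stands, although item 8 itself uses the word impact.

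**Conclusion.** The concern holds as a statement about what the analysis can do. As literally worded, item 8 relates a severity-driven exposure to a severity-driven outcome without a baseline term, and can make more medication look harmful when it helps. The reversal depends on a positive link between baseline severity and LED change. The protocol's treat-until-controlled rule makes that link plausible, but the documents do not quantify it. Within the assumed range the wrong sign runs from roughly a coin-flip at a correlation of 0.2 to nearly always at 0.6.

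A reader might infer that adding baseline adjustment would turn item 8 into a valid estimate of dose effect. It would not. Change alone carries regression to the mean, and adjustment for baseline leaves the confounding that arises when poor responders accumulate more changes. The gain is a less misleading description with its limits stated.

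The randomised primary comparison is untouched. The point deserves correction because item 8 serves the SAP's stated secondary objective.

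**What to change.** In SAP 3.4 item 8:

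1. Define the outcomes as change from baseline to 4 months in MDS-UPDRS Total and in BKS.
2. Report the association of each with amount of LED change and with number of medication changes, both unadjusted and adjusted for the corresponding baseline score and randomised arm. A Spearman partial correlation or a rank regression would do.
3. Label the analysis exploratory and non-causal. State that change alone is subject to regression to the mean, and that baseline adjustment does not remove confounding from poor responders receiving more changes, so that the adjusted correlation can still have the wrong sign.

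The cost is a few sentences and two covariates. Baseline MDS-UPDRS and PKG scores are already in the Protocol Table 1 schedule. Change needs both visits, so subjects whose baseline Part III was partial or missing because of COVID-19 (SAP 4.4) need the same handling as in the primary endpoint, and the number analysed may be somewhat below 41.

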3.5. Ancillary Endpoints

Ancillary endpoints will include measurements as indicated below:

- Rate of protocol defined adverse events affecting health care utilization including: hospitalizations, emergency department, urgent care or unanticipated clinic visits from at 4 months
- Rate of protocol defined adverse events and potential contraindications for increasing dopaminergic therapy including: falls, orthostatic hypotension, bothersome hallucinations, delirium, and impairment that prohibits interaction with the PKG watch at 4 months
- Rate of uncontrolled subjects in PKG+ group who are unable to be brought into Target Range through follow-up visits ($BKS \leq 25$ or $DKS \leq 9$). This will also be run for a threshold of a PKG score of $BKS \leq 26$ at 4-months.

4. Study Design

This is a prospective, multi-center, single-blind randomized (1:1) controlled, longitudinal follow-up study (1, 2, 3 years).

This is a randomized controlled trial (RCT) to evaluate treating uncontrolled patients with Parkinson's Disease (PwP) to a target range established by a published expert opinion manuscript. The study aims to evaluate clinical patient outcomes, quality of life measures and health care utilization of those patients specifically treated to a target range when using the PKG data in the clinical management of Parkinson's disease (PD) in routine clinical care (treatment group) compared to those managed with medical history and clinical evaluation alone (control group) performed by a neurologist experienced in PD management. Both groups will be recommended to undergo medication changes until they reach a "controlled state" that is determined by either the clinician using standard of care (SOC) (PKG- Group) or using PKG based targets and SOC assessments (PKG+ Group). For subjects in the treatment arm (PKG+ Group) the references will be according to the following table for purposes of analysis using PKG scores*:

	Target Range
Bradykinesia Score (BKS)	Median BKS 23-25
Dyskinesia Score (DKS)	Median DKS 7-9

The main objective of this study is to evaluate whether PwP who are managed with the aid of objective measurement and use of target ranges have improved PD symptoms and outcomes as compared to individuals treated using only standard of care (medical history, neurological examination).

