3.1. Primary Objective

This is a randomized controlled trial (RCT) to evaluate treating uncontrolled patients with Parkinson’s Disease (PwP) to a target range established by published expert opinion. The study aims to evaluate clinical patient outcomes, quality of life measures and health care utilization of those patients specifically treated to a target range when using the PKG data in the clinical management of Parkinson’s disease (PD) in routine clinical care (treatment group) compared to those managed with medical history and clinical evaluation alone (control group) performed by a neurologist experienced in PD management. Both groups will be recommended to undergo medication changes until they reach a “controlled state” that is determined by either the clinician using standard of

care (SOC) (PKG- Group) or using PKG based targets and SOC assessments (PKG+ Group). For subjects in the treatment arm (PKG+ Group) the references will be according to the following table for purposes of analysis using PKG scores. Subjects will either be considered bradykinetic (BKS scores exceed targets; BKS >25) or Dyskinetic (DKS scores exceed targets; DKS >9):

	Target Range
Bradykinesia Score (BKS)	Median BKS 23-25
Dyskinesia Score (DKS)	Median DKS 7-9

The main objective of this study is to evaluate whether PwP who are managed with the aid of objective measurement and use of target ranges have improved PD symptoms and outcomes as compared to individuals treated using only standard of care (medical history, neurological examination).

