An additional analysis will be conducted due to impacts from COVID-19 for the primary endpoint. This will include looking at instances where a partial UPDRS Part III was collected due to restrictions when conducting a telehealth video visit.

Subgroup Analysis of Primary Endpoint

Subgroup analyses will be conducted to examine the possible influence of baseline characteristics on the primary outcome. Subgroups of interest may include but are not limited to:

- Duration of disease – defined by years of disease (Date of Visit 1 - Year of PD Diagnosis)
- Stage of PD - defined by Hoehn & Yahr (1-5) at Visit 1
- History of fluctuation – defined by patient wearing off in last 30 days at Visit 1
- Gender
- Age – defined by Date of Visit - DOB
- Controlled PD at Baseline Visit in PKG+ and PKG- groups as defined by the PKG for both groups.
- Uncontrolled PD at Baseline Visit in PKG+ and PKG- groups as defined by the PKG for both groups.

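### SAP 3.5 counts a subject as brought into target if BKS ≤ 25 or DKS ≤ 9, which is not the complement of the out-of-target rule in SAP 3.1; the connective should be *and*

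*SAP*

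**What the plan says.** SAP 3.1 sets the classification: "Subjects will either be considered bradykinetic (BKS scores exceed targets; BKS >25) or Dyskinetic (DKS scores exceed targets; DKS >9". A subject is therefore out of target if either score is above its upper cut.

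SAP 3.5 lists, among the ancillary endpoints, the "Rate of uncontrolled subjects in PKG+ group who are unable to be brought into Target Range through follow-up visits". A parenthesis after it gives the criterion as BKS ≤ 25 or DKS ≤ 9. The same bullet adds: "This will also be run for a threshold of a PKG score of" BKS ≤ 26 at 4 months, with no DKS term.

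Two other places need the same classification:

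- SAP 3.4 item 7 plans summaries "for controlled (in target range) and uncontrolled (out of target range) in PKG+ and PKG- groups", and a rate of subjects uncontrolled at baseline who are controlled at 4 months, described as "PKG Summary Scores reduced to below targets".
- SAP 3.2 lists a subgroup of the primary endpoint as "Uncontrolled PD at Baseline Visit in PKG+ and PKG- groups as defined by the PKG for both groups", with a matching controlled subgroup.

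Neither place says how the two scores combine.

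In the protocol, control is judged differently by arm. In section 4.5, "for PKG+ group subjects, this is per the Acceptable Target Range", and that table attaches fluctuation score (FDS) conditions to both rows, including FDS < 13 in the dyskinesia row. The SAP tables carry no FDS term. The SAP introduces its table with "the references will be according to the following table for purposes of analysis using PKG scores".

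**The concern.** The endpoint is meant to show how often treating to target failed to reach the target. Subjects enter the denominator because they are out of target, so they should leave the failure count only when they are no longer out of target. With *or* in the attainment rule, a subject can be out of target by SAP 3.1 and attained by SAP 3.5 at the same visit.

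The result is a failure rate that is too low. On one reading it counts subjects who never improved as reaching target. On the other it counts subjects whose bradykinesia was treated at the price of dyskinesia. Protocol 4.5 allows up to four medication changes, and Protocol 1.0 notes that dopaminergic treatment can itself cause motor complications, so the second outcome is one this endpoint should be able to show.

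**Working it through.** The plan gives no expected rate or precision for this endpoint, so there is no figure to reproduce. The check is one of logic, followed by an illustration of scale.

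**Step 1: the complement.** Out of target (SAP 3.1) is BKS > 25 or DKS > 9. Its negation is BKS ≤ 25 and DKS ≤ 9. SAP 3.5 prints BKS ≤ 25 or DKS ≤ 9.

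**Step 2: the four possible outcomes at follow-up**, with example scores.

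| BKS, DKS | Out of target in 3.1? | 3.5 read literally | 3.5 by type, bradykinetic subject (BKS only) | 3.5 by type, dyskinetic subject (DKS only) | *And* rule |
|---|---|---|---|---|---|
| 24, 8 | no | attained | attained | attained | attained |
| 24, 15 | yes | attained | attained | failed | failed |
| 30, 8 | yes | attained | failed | attained | failed |
| 30, 15 | yes | failed | failed | failed | failed |

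The literal rule contradicts 3.1 in 2 of the 4 outcomes. The by-type rule contradicts it in 1 of 4 for each type. These are kinds of outcome, not frequencies.

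**Step 3: what each reading does.**

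- Literal: a subject at BKS 30, DKS 8 is bradykinetic in 3.1 but already meets the 3.5 rule at baseline. Only subjects above both cuts can fail.
- By type: that subject is scored correctly. A bradykinetic subject who goes from BKS 30 to 22 while DKS rises to 15 is counted as attained, although 3.1 calls that subject dyskinetic. A subject above both cuts at baseline belongs to both types, and the SAP does not say which score decides.

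**Step 4: scale, on assumed inputs.** Let N be the uncontrolled PKG+ subjects, each starting above one cut only. Let n1 end above exactly one cut, n2 above both, and let c of the n1 be crossers (in on the score they started out on, now out on the other). The failure rates are:

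- *And* rule: (n1 + n2)/N
- Literal: n2/N, which is too low by n1/N
- By type: (n1 + n2 − c)/N, which is too low by c/N

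For N, 41 enrolled at 1:1 gives about 20 in PKG+. Taking 78% as uncontrolled (the earlier cohort in Protocol 1.0), 0.78 × 20 = 15.6, rounded to 16. N = 10 is a lower alternative. The values of n1 and n2 are invented. Intervals are exact (Clopper-Pearson) 95%.

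| Assumed N, n1, n2 | Literal | *And* rule |
|---|---|---|
| 16, 4, 0 | 0/16 = 0% (0 to 20.6%) | 4/16 = 25.0% (7.3 to 52.4%) |
| 16, 8, 0 | 0/16 = 0% (0 to 20.6%) | 8/16 = 50.0% (24.7 to 75.3%) |
| 10, 4, 0 | 0/10 = 0% (0 to 30.8%) | 4/10 = 40.0% (12.2 to 73.8%) |

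In the first row the by-type rate is (4 − c)/16. With no crossers it equals the *and* rule, and each crosser lowers it by 1/16 = 6.25 percentage points.

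**Step 5: direction.** Every subject who passes the *and* rule also passes 3.5 on either reading. The correction can therefore only raise the failure rate or leave it unchanged.

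**The case against.** The best defence is that *or* means *respectively*. SAP 3.1 sorts subjects as either bradykinetic or dyskinetic, SAP 3.5 starts from uncontrolled subjects, and the parenthesis can be read as pairing each type with its own cut. The BKS ≤ 26 run, with no DKS term, fits that reading. A literal reading that empties the endpoint is itself a reason to doubt it. This is plausible and makes the problem much milder, but the SAP does not state it, and it still misscores crossers and leaves subjects above both cuts without a clear rule.

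It can also be said that SAP 3.4 reports BKS, DKS and FDS changes separately, so a rise into dyskinesia would be visible there. That is true, but it does not correct this rate. In 3.4 item 7 the plural wording about scores falling below targets is compatible with requiring both; it does not say so. Appendix 2, the statistical tables, is an attachment not among the documents reviewed and might specify the flag. It cannot be assumed to override the printed text.

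A reader might also infer that dropping FDS is an analysis error. The documents do not support that. The SAP openly sets its own table for analysis, FDS is still analysed as a change score, and the protocol's bradykinesia row joins its FDS condition with *and/or*, which cannot be programmed without an interpretation. A subject at BKS 24, DKS 8, FDS 14 does miss the protocol's dyskinesia row and pass 3.5, but what is missing is a stated reason. The lower limits (23 and 7) are similar: the tables show them, while the operative wording in 3.1, 3.4 and 3.5 uses upper cuts.

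**Conclusion.** The point holds: the printed attainment rule does not match the SAP's own out-of-target rule on either reading. Its size depends on the reading. Taken literally, every subject who ends above exactly one cut is misscored. Taken by type, only those who cross are misscored.

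The number of subjects affected cannot be computed, because the documents give no joint distribution of BKS and DKS. The 0% against 25 to 50% contrasts above apply to the literal reading only and rest on assumed counts. The 78% comes from a cohort with low access to specialist care whose out-of-target definition also included tremor, so it is not a rate for these cuts.

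Two stronger conclusions are tempting and not supported. One is that subjects who do not improve will be reported as successes: that follows only if the rule is programmed literally. The other is that the trial's main result is compromised: the primary intention-to-treat comparison of MDS-UPDRS change does not use this flag. What is affected is one descriptive ancillary rate in about 20 PKG+ subjects, together with the control rate in SAP 3.4 item 7 and the control subgroups in SAP 3.2 if they take the same rule.

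**What to change.** - In SAP 3.5, replace *or* with *and*, so that attainment is BKS ≤ 25 and DKS ≤ 9. This is the exact complement of SAP 3.1 and also settles subjects above both cuts.
- Use the same flag for the uncontrolled-to-controlled rate in SAP 3.4 item 7 and for the PKG-defined control subgroups in SAP 3.2.
- Run the sensitivity threshold as BKS ≤ 26 and DKS ≤ 9, so that it relaxes only the bradykinesia cut.
- Optionally, as a labelled sensitivity analysis, also require FDS < 13 as in the protocol's dyskinesia row. This can only add failures.

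The cost is a change of SAP wording and one derived variable. No new data are needed, since FDS is already collected. The optional analysis adds one descriptive rate to report.
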